#### Prenatal procedures:

All participants will be followed-up during the pregnancy applying following procedures:

- Questionnaires to evaluate sociodemographic, health and habits background. This questionnaire will be answered during the first trimester of pregnancy.
- SCL-90 (Symptom Checklist): In order to evaluate mental health. This questionnaire will be filled during the first trimester of pregnancy.
- AUDIT-C (Assessment of the Alcohol use disorders identification test): To evaluate ethanol intake. This questionnaire will be filled during first trimester of pregnancy and also up to 7 days after delivery.
- Fetal neurosonography: To evaluate fetal neurodevelopment and brain structure at 28 and 32 weeks of gestation through transabdominal and transvaginal exploration using a General Electric Voluson E10 sonograph (GE Medical Systems, Zipf, Austria).
- Biological samples: Samples will be collected at the moment of delivery to obtain to different biomarkers :
  - o Ethylglucuronide (EtG) on mother's hair: In order to evaluate chronic ethanol intake.
  - o Phosphatidylethanol (PEtH) on dried cordblood spot: In order to evaluate ethanol intake during last 3 weeks prior delivery.

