#### Sample size

Assuming a prevalence of ethanol consumption in our environment of at least 40% in the control group and about 25% (or less) in the intervention group. Thus, about 240 of prenatally exposed children will be followed up in their postnatal period. According to previous experience cohort studies, we may assume a maximum of 30% of loss during their ambulatory control. Regarding this estimate, 168 children will complete their follow up. This sample size can ensure a 90% of potency to detect differences of prevalence between both groups, with a signification of 5%.

Values were corrected regarding number of clusters (n= 8) and intraclass correlation coefficient. Intraclass correlation coefficient was estimated regarding the prevalence of ethanol intake among groups.

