### Randomization and intervention

Under a sequential rollout, 8 clusters (primary care centers from a geographic location of Barcelona; Baix Llobregat) were randomly allocated according to a random number generator with a fixed seed, using R Core Team (2018). R: A language and environment for statistical computing. R Foundation for Statistical Computing, Vienna, Austria. URL <https://www.R-project.org/>, to incorporate a MI program into existing prenatal care visits (intervention group) or usual intervention (control group). The allocation was performed by a statistician. Midwives from centers allocated to perform MI were trained by an expert team. Participants enrolment was performed by midwives of both groups (interventional and control group). This is a simple masking study, it means that participants will not aware of the allocation and intervention.

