### Outcomes

The primary outcome of the study is to demonstrate the effectiveness of repetitive MI to reduce alcohol intake. This will be measured by the presence of ethanol intake biomarkers (EtG in mother's hair and Peth in cordblood).

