### Statistical analysis

Analysis will be conducted by intention-to-treat. Missing data for the main outcome will be handled by complete data analysis because women without an answer on the main outcome will be excluded. All analyses will be divided by groups (control vs experimental group). Continuous data will be assessed for normality using the Kolmogorov-Smirnoff test. Normally distributed variables will be compared among groups using t-test and expressed as mean and standard deviation (SD), while not normally distributed variables will be compared using the Mann-Whitney-U test and expressed as medians and interquartile range (IQR). Quantitative variables will be compared using  $\chi^2$  test and expressed as counts (n) and proportions (%). For categorical variables Fisher exact test or Chi-squared test are used. Regarding demographic data (age, sex, body mass index (BMI), etc.); continuous variables will be presented as mean and SD, or median and IQR, according to their distribution, and categorical variables as percentages (%).

For the main outcome, differences in prevalence of ethanol intake between groups will be analyzed using absolute risk increase defined as the incidence of the outcome in the experimental group minus the incidence in the control group. The absolute risk increase will be depicted in a forest plot. A multivariate logistic regression will be performed to determine the Odds Ratio for ethanol intake adjusting by demographic characteristics. Data will be analyzed using R Core Team (2018). R: A language and environment for statistical computing. R Foundation for Statistical Computing, Vienna, Austria. URL <https://www.R-project.org/> and GraphPad Prism version 8.1.2, GraphPad Software, San Diego, California USA, [www.graphpad.com](http://www.graphpad.com).

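### The 90% power claim for 40% versus 25% does not follow from the 168 or 240 children it is attached to, and the number of women in the primary comparison is never stated

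*Combined protocol and SAP*

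**What the plan says.** The Sample size section sets the prevalence of alcohol consumption at 40% or more in the control group and about 25% or less in the intervention group. It continues: "Thus, about 240 of prenatally exposed children will be followed up in their postnatal period". Allowing at most 30% loss in that period, it expects that "168 children will complete their follow up". The next sentence is the power claim: "This sample size can ensure a 90% of potency to detect differences of prevalence between both groups, with a signification of 5" per cent. The section then says "Values were corrected regarding number of clusters (n= 8) and intraclass correlation coefficient", with the ICC estimated from prevalence. It gives no ICC value, design effect, per-arm number, sidedness or count of women.

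The primary outcome is defined elsewhere. Under Outcomes, the effect on alcohol intake is judged as follows: "This will be measured by the presence of ethanol intake biomarkers", namely EtG in maternal hair and PEth in cord blood. Under Prenatal procedures, "Samples will be collected at the moment of delivery to obtain to different biomarkers". Under Statistical analysis, "women without an answer on the main outcome will be excluded". Randomization and intervention adds "Under a sequential rollout, 8 clusters", without saying how many centres are in each arm.

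**The concern.** Two things look wrong. First, 168 and 240 are too few for 90% power at 40% versus 25% if either is the total analysed, even without clustering. Second, neither is a natural denominator for the primary outcome. Both count exposed children followed after birth, and the 30% is loss after birth, whereas the biomarker samples are taken at delivery. Nor can the prevalence of exposure be compared between arms among children who are all exposed.

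This is the plan's only power statement for the primary outcome. On one reading the planned effect would be missed about 45% of the time rather than 10%; on another the 90% stands. A reader cannot tell which applies, so a non-significant result could be taken as strong evidence against motivational interviewing on the strength of a figure that cannot be checked.

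**Working it through.** **Inputs from the Sample size section:** p1 = 0.40, p2 = 0.25, significance 5%, claimed power 90%, 240 children, 30% loss, 8 clusters. The loss step reproduces: 240 × 0.70 = 168.

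**Assumptions not in the plan:** 1:1 allocation; a parallel design with 4 centres per arm; a two-sided test unless stated; every ICC value.

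**Formula** (pooled two-proportion normal approximation, n per arm, p̄ = 0.325):

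power = Φ{ [0.15 − z·√(2p̄(1−p̄)/n)] / √[(0.40×0.60 + 0.25×0.75)/n] }

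- n = 84 (168 in total): (0.15 − 0.1417)/0.0713 = 0.117, so power is 54.7%.
- n = 120 (240 in total): (0.15 − 0.1185)/0.0597 = 0.528, so power is 70.1%.
- n for 90%: [1.960×√(2×0.325×0.675) + 1.282×√0.4275]² / 0.15² = (1.298 + 0.838)²/0.0225 = 202.8 per arm, about 406 women.

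**Can another method rescue the stated totals?** One-sided power is 66.9% (168) and 80.1% (240). Continuity correction, unpooled variance, the arcsine method and unequal allocation were also tried. The highest result was about 81% (240, one-sided, unpooled). A 3:5 split of centres gives 51–53% (168) and 67–68% (240), two-sided.

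**Clustering.** Divide n by DE = 1 + (m − 1)×ICC, with m = N/8.

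| Total N | m | ICC 0 | ICC 0.01 | ICC 0.05 |
|---|---|---|---|---|
| 168 | 21 | 54.7% | 47.4% (DE 1.20) | 30.9% (DE 2.00) |
| 240 | 30 | 70.1% | 59.0% (DE 1.29) | 35.2% (DE 2.45) |

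**Readings that do reach 90%.** Each needs something the plan does not state.

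| Reading | Power at ICC 0 | 90% holds up to ICC of about |
|---|---|---|
| 168 per arm, one-sided | 90.4% (83.8% two-sided) | 0.0004 |
| 240 per arm, two-sided | 94.2% | 0.003 |
| 168 exposed: 168/0.325 ≈ 517 women, two-sided | 95.6% | 0.004 |
| 240 exposed: 240/0.325 ≈ 738 women, two-sided | 99.2% | 0.009 |

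For 738 women, m ≈ 92.3. An ICC of 0.009 gives DE 1.82 and 90.0% power; 0.01 gives 88.5% and 0.02 gives 73.8%.

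**How much the missing ICC matters.** Women needed for two-sided 90%: about 406 at ICC 0, 507 at 0.004 and 815 at 0.01. As centres grow, the effective number per arm cannot exceed 4/ICC, so 90% is out of reach for any number of women once the ICC passes 4/202.8 ≈ 0.020.

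**The case against.** The strongest reply is that 55% and 70% are powers for a comparison the plan's words exclude. If the 240 are exposed children, they are a subset of a larger cohort. At 1:1 that implies about 738 women, with 99.2% power before clustering. A cluster correction that brings this down to 90% would be consistent with the statement that the figures were corrected. The 30% loss falls after delivery, so it need not touch the primary comparison, and the sample size credited with 90% may be that larger cohort rather than the 168. On this view the claim is unverifiable rather than wrong.

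Part of this stands. It shows that the trial's true power may be adequate, and that 55% must not be read as that power. It does not rescue the statement: 738 appears nowhere, the ICC it needs (up to about 0.009) appears nowhere, and the sentence claiming 90% directly follows the 168.

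The prevalences are also worded as bounds, so a larger difference is possible. Unclustered 90% would need the intervention arm at 17.6% (168 in total) or 20.9% (240) against 40%, or the control arm at 48.8% or 44.8% against 25%. These are not the planning values.

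Two technical cautions are fair. A positive ICC lowers power as shown only in a parallel design; the mention of a sequential rollout leaves the design open. And the ICC limits come from a normal approximation with only 8 clusters, so they are approximate.

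**Conclusion.** The concern holds. With 168 or 240 as the analysed total, the plan's own prevalences give about 55% or 70% power two-sided, and 67% or 80% one-sided, before clustering; no standard method reaches 90%. This part assumes roughly equal arms. Separately, and whatever formula or ICC is used, the claim is tied to exposed children completing postnatal follow-up and not to women with a biomarker result at delivery, whose number is not given.

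Confidence is high that the 90% does not reproduce as written. It is not a finding that the trial is underpowered: with about 738 women and an ICC up to about 0.009, 90% would hold.

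**What to change.** Rewrite the sample-size paragraph for the primary outcome. State:

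- the number of women expected to have a biomarker result at delivery, with any allowance for missing samples;
- centres per arm, and how the sequential rollout enters the calculation;
- the numeric ICC, its source and the design effect;
- whether the test is one- or two-sided;
- the resulting power, or the difference detectable with 90% power.

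Withdraw the 90% claim for 168 completers, and keep 90% only if the recalculation for women analysed at delivery supports it. Describe the 240/168 postnatal cohort in its own paragraph, with its own statement of precision.

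The cost is one paragraph, with no new data and no extra enrolment. The stated power may turn out less favourable.

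### The 90% power rests on a cluster correction whose ICC is not printed and, as worded, reflects the assumed effect of motivational interviewing (MI) rather than variation between centres; the stated totals do not give 90% on either reading

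*Combined protocol and SAP*

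**What the plan says.** All the planning figures are in the Sample size section of the combined protocol and SAP. The assumed prevalences of ethanol intake are "at least 40% in the control group and about 25% (or less) in the intervention group". The plan then says that "about 240 of prenatally exposed children will be followed up in their postnatal period", allows 30% loss, arrives at 168 completers and concludes: "This sample size can ensure a 90% of potency to detect differences of prevalence between both groups", at 5% significance.

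Two sentences cover clustering. The first is "Values were corrected regarding number of clusters (n= 8) and intraclass correlation coefficient". The second is "Intraclass correlation coefficient was estimated regarding the prevalence of ethanol intake among groups". The section gives no ICC value, design effect, number of women per centre, number of centres per arm or data source for the ICC.

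On vocabulary, the Statistical analysis section says "All analyses will be divided by groups (control vs experimental group"). Interventions and procedures, Postnatal procedures and Randomization and intervention use *group* for the arms in the same way. The randomised units are called clusters or centres, including in the sentence just before the one on the ICC.

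**The concern.** The correction for cluster randomisation needs the ICC between centres that share an allocation, that is, how far drinking prevalence differs from centre to centre within an arm. A contrast between the arms is the assumed treatment effect. An ICC built from it rises as MI is assumed to work better, and it carries no information about how alike women in one centre are.

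If the wrong quantity went into the correction, or a quantity that cannot be checked, the 90% has no visible support. A non-significant result could then be read as good evidence that MI does not work, from a trial whose real power may have been much lower. With few clusters the number of centres also limits power. Above a certain ICC, more women in the same 8 centres cannot restore 90%.

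**Working it through.** **Inputs from the plan.** Control prevalence 0.40; intervention prevalence 0.25; difference 0.15; significance 5%; power 90%; 8 clusters; 240 children falling to 168 (240 × 0.7).

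**Assumptions, because the plan is silent.** Two-sided test; 4 centres per arm; equal centre sizes; unpooled variance v = 0.40 × 0.60 + 0.25 × 0.75 = 0.4275. Two test bases are shown: a normal test, and a t test on 6 df (8 centres minus 2).

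**1. Try to reproduce the 90% without clustering.** Women needed per arm = (1.960 + 1.2816)² × 0.4275 / 0.15² = about 200, or about 400 in total. With n per arm, power is Φ(0.15/√(0.4275/n) − 1.96).
- 168 in total (n = 84): 0.15/√(0.4275/84) = 2.10, power 56%.
- 240 in total (n = 120): 0.15/√(0.4275/120) = 2.51, power 71%.

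A pooled-variance formula gives 203 per arm, and 55% and 70%. One-sided (pooled), the powers are 67% and 80%. None of these variants gives 90%, even before any loss to clustering.

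**2. ICC implied by the arm prevalences.** The mean prevalence is 0.325 and each arm lies 0.075 from it. ICC = 0.075² / (0.325 × 0.675) = 0.0256. With an n − 1 variance between the two arms it is about 0.05.

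**3. Ceiling with 4 centres per arm.** With m women per centre the design effect is 1 + (m − 1) × ICC. As m grows, the effective number per arm cannot exceed 4/ICC. At 0.0256 that is 156, below the 200 needed. The standard error tends to √(0.4275 × 0.0256/4) = 0.0523, and 0.15/0.0523 = 2.87. Power is then at most Φ(2.87 − 1.96) = 82% by the normal test, or 67% by a noncentral t on 6 df. Pooled variance gives 81% for the normal figure and 88.5% one-sided.

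**4. Largest ICC at which 8 centres can reach 90%.** ICC limit = 4 × 0.15² / (0.4275 × λ²), where λ is the noncentrality needed for 90% power.
- Normal: λ = 1.960 + 1.2816 = 3.24; limit 0.09/(0.4275 × 10.51) = 0.020.
- t on 6 df: λ = 3.91; limit 0.09/(0.4275 × 15.31) = 0.014.

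For scale, an ICC of 0.02 around 40% is a between-centre SD of √(0.02 × 0.24) = 0.069, about 7 percentage points.

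**5. Power by total and ICC.** If the 240 counts exposed children only, the number of women at the mean prevalence would be 240/0.325 = about 738. This is an assumption; the plan gives no such total. Each cell is normal / t on 6 df.

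| ICC | 168 | 240 | 738 | No limit on women |
|---|---|---|---|---|
| 0 | 56% / 42% | 71% / 56% | 99% / 95% | – |
| 0.01 | 48% / 37% | 60% / 46% | 89% / 76% | 99.6% / 97% |
| 0.02 | 43% / 32% | 52% / 39% | 75% / 59% | 90% / 77% |
| 0.0256 | 40% / 30% | 48% / 36% | 67% / 53% | 82% / 67% |
| 0.05 | 32% / 24% | 36% / 27% | 46% / 35% | 54% / 41% |

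Example for 240 at ICC 0.01: m = 30, design effect 1 + 29 × 0.01 = 1.29, effective n per arm 120/1.29 = 93, 0.15/√(0.4275/93) = 2.21, power 60%.

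**The case against.** A reader might infer that the sponsor did build the ICC from the arm contrast, and that 90% power is therefore impossible in this trial at any enrolment. The documents do not support that.

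- No ICC is printed, so 0.0256 is what the wording implies and not a figure from the plan.
- The English of the document is loose, and *groups* may have meant centres. The sentence could also mean that an ICC for a binary outcome was scaled to the assumed prevalences.
- An ICC that makes 90% impossible is unlikely to be the one that produced a stated 90%. It is as plausible that another value was used, or that no workable correction was made.
- Below the limits in step 4, 8 centres can reach 90% if enough women are analysed.

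All of this stands, and it makes the impossibility conditional on one reading.

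The ceilings also rest on choices that the plan does not make. The 4:4 split is assumed, and a test on 6 df is not specified in the Statistical analysis section. The 15-point difference is the smallest the plan allows, since it says at least 40% and 25% or less. At 40% versus 20% (an illustration) the limits rise to 0.16/(0.40 × 10.51) = 0.038 (normal) and 0.16/(0.40 × 15.31) = 0.026 (t, 6 df).

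These points do not reduce the matter to a reporting gap. On the plan's own 40% and 25%, neither 168 nor 240 gives 90% even with no clustering, and any positive ICC lowers the power further. That holds whatever *groups* meant.

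**Conclusion.** The concern holds in conditional form. As worded, the ICC source is the assumed MI effect, which is not a valid input to a design effect, and no value is printed that could show otherwise.

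- **If the ICC came from the arm prevalences:** it is about 0.026, and with 4 centres per arm the power cannot exceed about 82% (normal) or 67% (t, 6 df).
- **If *groups* meant centres:** 90% needs a within-arm ICC below about 0.020 (normal) or 0.014 (t, 6 df), and far more women than the stated totals. Totals of 168 and 240 give about 56% and 71% at ICC 0, and 48% and 60% at ICC 0.01 (normal, two-sided). The assumed 738 women give about 89% (normal) or 76% (t, 6 df) at ICC 0.01.

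On either reading the stated 90% does not follow from the plan's own figures. This rests on a two-sided 5% test, equal centres split 4:4, and a 15-point difference. Which side of the ICC limits the trial falls on cannot be told from the documents.

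**What to change.** In the Sample size section:

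1. Replace the ICC sentence with a within-arm, between-centre ICC for biomarker-positive intake. Take it from centre-level data before the intervention or from external data, not from the 40% versus 25% contrast. Print the value and its source.
2. State the number of centres per arm and the number of women analysed for the primary outcome, kept distinct from the number of exposed children followed up.
3. Replace the flat 90% with the power that 8 centres give over a range of ICCs, for example 0.01 to 0.05. Name the test basis and quote the limit that belongs to it: about 0.020 for a normal test, about 0.014 for a t test on 6 df. The two should not be mixed.

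The cost is a rewritten paragraph, one recalculation and a less favourable stated power. No extra enrolment and no change to conduct is proposed.

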### Randomization and intervention

Under a sequential rollout, 8 clusters (primary care centers from a geographic location of Barcelona; Baix Llobregat) were randomly allocated according to a random number generator with a fixed seed, using R Core Team (2018). R: A language and environment for statistical computing. R Foundation for Statistical Computing, Vienna, Austria. URL <https://www.R-project.org/>, to incorporate a MI program into existing prenatal care visits (intervention group) or usual intervention (control group). The allocation was performed by a statistician. Midwives from centers allocated to perform MI were trained by an expert team. Participants enrolment was performed by midwives of both groups (interventional and control group). This is a simple masking study, it means that participants will not aware of the allocation and intervention.

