### Interventions and procedures

For the experimental group, the intervention consists in a MI program during prenatal care visits. MI will be received at least one time each trimester of pregnancy.

For the control group, usual prenatal care attention will be given, but they will be directly asked sign a consent form.

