### Intervention: Motivational interview

The MI is integrated in a structure theoretical mark. This method is a person-centered counseling style that increases the intrinsic motivation of the patient to behavioral changes through spirit, acceptance, compassion and evocation. Furthermore, it is a low-cost methodology, and any professional or individual could have been capacitated. Since the motivational interview is a good cost benefit intervention, it is a potential and suitable tool to implement in a healthcare public program.

Professionals whose attend prenatal care visits at centers allocated to give MI will receive previous capacitation (15 hours) dictated by a multidisciplinary expert group who are dedicated several years to MI training and addiction disabilities. This training group is composed by a psychiatrist and a psychologist from *Addictions Unit of Psychiatry Department of Clínic Hospital of Barcelona*

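### Enrolment by midwives who, in the MI arm, apparently already knew their centre's allocation can leave the arms unequal in drinking before any MI, and neither primary estimate adjusts for baseline drinking

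*Combined protocol and SAP*

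**What the plan says.** On allocation and recruitment, the Randomization and intervention section states that "8 clusters (primary care centers from a geographic location of Barcelona; Baix Llobregat) were randomly allocated". It then says "Midwives from centers allocated to perform MI were trained by an expert team" and "Participants enrolment was performed by midwives of both groups (interventional and control group"). The section on the motivational interview adds: "Professionals whose attend prenatal care visits at centers allocated to give MI will receive previous capacitation (15 hours").

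On masking: "This is a simple masking study, it means that participants will not aware of the allocation and intervention". No masking of recruiters is described.

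On who may enter, the Participants section excludes women unwilling to take part, in either arm. No section describes consecutive invitation, a screening log, or a recruiter independent of the centre.

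On timing, Interventions and procedures calls for MI at least once in each trimester. Of AUDIT-C, Prenatal procedures says: "This questionnaire will be filled during first trimester of pregnancy and also up to 7 days after delivery". The biomarkers that define the primary outcome are collected at delivery.

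On analysis, the main contrast is the incidence in the experimental group minus that in the control group, with no adjustment mentioned. In addition, "A multivariate logistic regression will be performed to determine the Odds Ratio for ethanol intake adjusting by demographic characteristics".

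**The concern.** Randomising centres balances the centres, in expectation. It does not protect the comparison of women if they are recruited afterwards by staff who know what their centre was assigned. Whoever decides which women to approach can, without intending to, bring in a different mix of drinkers and non-drinkers in one arm. The arms then differ in the outcome behaviour before MI has been given. Intention-to-treat does not help, because the selection happens before a woman enters the analysis set.

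A drinking measure taken before MI would show the imbalance and allow partial correction. AUDIT-C is the obvious candidate, but the plan neither fixes its order relative to the first MI nor names it as a covariate. What is at stake is whether a lower prevalence in the MI arm can be read as an effect of MI, or a null result as its absence.

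**Working it through.** **Sequence implied by the text**

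1. Training is given to staff of centres already allocated to MI, and is described as prior. Allocation therefore precedes training, and trained midwives know their arm.
2. The enrolling midwives are described by arm, so the arms existed when enrolment took place. No dates are given; enrolment after allocation is an inference, though the natural one.
3. MI is due in the first trimester and AUDIT-C is taken in the first trimester, with no order set. In the MI arm AUDIT-C may come before or after the first MI. In the control arm the question does not arise.

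**Benchmark from the plan**

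The Sample size section assumes 40% drinking in the control group and 25% in the intervention group: 40 − 25 = 15 points. The plan gives no figure for recruitment by drinking status, so the enrolment rates below are assumptions.

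**Drinkers under-enrolled in MI centres, no MI effect**

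True prevalence is 40% in both arms. Control enrolment is unrelated to drinking. Non-drinkers in MI centres enrol at 80% and drinkers at rate c.

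Enrolled MI-arm prevalence = 0.4c / (0.4c + 0.6 × 0.8)

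| c | Calculation | Enrolled prevalence | Spurious reduction | Share of 15 points |
|---|---|---|---|---|
| 70% | 0.28 / 0.76 | 36.8% | 3.2 points | 21% |
| 60% | 0.24 / 0.72 | 33.3% | 6.7 points | 44% |
| 50% | 0.20 / 0.68 | 29.4% | 10.6 points | 71% |

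**Drinkers over-enrolled in MI centres, real MI effect**

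Reverse the rates: drinkers enrol at 80% and non-drinkers at rate u. Pre-MI prevalence is 0.32 / (0.32 + 0.6u). Suppose MI then has the planned proportional effect, 25/40 = 0.625.

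| u | Pre-MI prevalence | After MI (× 0.625) | Observed reduction from 40% |
|---|---|---|---|
| 70% | 0.32 / 0.74 = 43.2% | 27.0% | 13.0 points |
| 60% | 0.32 / 0.68 = 47.1% | 29.4% | 10.6 points |
| 50% | 0.32 / 0.62 = 51.6% | 32.3% | 7.7 points |

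A true 15-point effect would be reported as 13.0, 10.6 or 7.7 points.

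**Effect on the test**

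If MI does nothing but the MI arm starts d points lower, the two-sided 5% pooled test rejects with probability Φ((d − 1.96·s₀)/s₁) + Φ((−d − 1.96·s₀)/s₁). Here s₀ = √(2p̄(1 − p̄)/n), s₁ = √((p₁(1 − p₁) + p₂(1 − p₂))/n), p₁ = 0.40, p₂ = 0.40 − d, p̄ is their mean and n is the number per arm.

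For d = 0.05 and n = 120: p̄ = 0.375, s₀ = 0.0625, s₁ = 0.0624, giving 0.126.

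| n per arm | d = 5 points | d = 10 points |
|---|---|---|
| 84 (168/2) | 10% | 27% |
| 120 (240/2) | 13% | 37% |

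The arm sizes assume an even split of the plan's 168 and 240, and the calculation ignores clustering. It shows how a modest starting imbalance inflates a nominal 5% error rate; it does not estimate the error rate of this trial.

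**The case against.** The strongest reply is that participants are masked. If that works, women have little arm-specific reason to refuse, so a reader who infers that drinkers would decline more often in MI centres goes beyond the text. This stands as far as it goes, and it leaves selective invitation by midwives as the main route. The arithmetic applies to that route, because the rates are rates of enrolment, however it fails.

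Four further inferences are tempting and not supported:

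- **That consent differed by arm.** Interventions and procedures mentions consent only for controls, who "they will be directly asked sign a consent form". But the exclusion of unwilling women applies to both arms, and the consent pages are not part of the reviewed text. The sentence is not evidence of unequal consent.
- **That every recruiter knew the allocation.** This follows for MI midwives from their training. Control midwives' knowledge is not stated.
- **That bias would favour MI.** Trained midwives might equally seek out drinkers. The direction is unknown.
- **That AUDIT-C was in fact taken after MI.** The plan leaves the order open and says no more.

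It can also be said that eligibility criteria are common to both arms, and that all women complete a first-trimester questionnaire on habits. Common criteria do not determine who is invited. The habits questionnaire might help to reveal imbalance, but its order relative to MI is unstated too.

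**Conclusion.** The concern holds as a gap in protection, not as a demonstrated bias. The documents imply recruitment after allocation by midwives who, in the MI arm, knew their assignment. They describe no safeguard on whom midwives invite, and they plan two primary estimates that cannot correct an imbalance in prior drinking.

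Under the assumed enrolment rates, selection alone could yield between 21% and 71% of the planned difference, or cut a true 15-point effect to between 13.0 and 7.7 points. These figures rest on the plan's 40% and 25%, on control enrolment being unrelated to drinking, and on enrolment rates that do not come from the documents. The second range also assumes a proportional MI effect. Neither the size nor the direction of any actual selection can be established from the plan.

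**What to change.** **Procedures.** In Prenatal procedures and Randomization and intervention, require invitation of consecutive first-trimester attenders by the same procedure in both arms, with consent and AUDIT-C completed before the first MI contact.

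**Analysis.** In Statistical analysis, add this baseline AUDIT-C to the demographic covariates and apply the adjustment to both primary estimates: the odds ratio, and the risk difference (for example by standardisation from the same model). Adjusting the logistic model alone would leave the risk difference exposed.

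**Reporting.** Give baseline AUDIT-C and the enrolled fraction of eligible attenders by centre and arm. State that similar fractions do not rule out selection, since they do not show the drinking status of women not enrolled.

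**Women already enrolled.** The plan describes enrolment in the past tense, so the procedural changes may come too late for some. Do not exclude women whose AUDIT-C followed MI: control women receive no MI, so such exclusions could fall in the MI arm only and would create a new selection bias. Report how many there are, as far as contact dates allow, and give results with and without AUDIT-C adjustment.

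**Cost.** A slightly longer first visit and one more covariate. AUDIT-C is self-reported, so adjustment reduces the bias but does not remove it.
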